Appendix 3: Total Blood Volume

The following blood volumes will be withdrawn for each subject:

Assessment	Approximate Blood Volume per Sample (mL)	Maximum Number of Blood Samples	Approximate Total Volume (mL)
Serology	8.0	1	8.0
Hemoglobin A1c (HbA1c)	4.0	1	4.0
Probe drug cocktail pharmacokinetic (PK) sampling ^a	4.0	36	144.0
LOXO-305 PK sampling	4.0	30	120.0
Clinical laboratory evaluations:			
Hematology	4.0	9	
Clinical chemistry ^b	4.0	9	
Coagulation	3.0	9	
Serum pregnancy test (female subjects only)	4.0	3	12.0
Serum follicle-stimulating hormone (post- menopausal female subjects only)	4.0	1	4.0
Genotyping	14.0	1	14.0
Total:			405.0 mL

^aFor PK samples for analysis of each substrate (caffeine/paraxanthine, omeprazole, and S-warfarin) a single blood sample will be collected.

^b Thyroid-stimulating hormone (TSH) and estimated glomerular filtration rate (eGFR) will be assessed as part of the clinical chemistry sample.

If extra blood samples are required, the maximum blood volume to be withdrawn per subject will not exceed 500 mL.

Appendix 4: Schedule of Assessments

Study Procedures ^a	Screening (Days -35 to -2)	Check-in (Day -1)	Period 1					Period 2															Clinic Discharge EOT/ET ^u	Follow-up phone call (EOS)	
			1	2	3	4	5	6	7	8	9	10	11	12	13	14	15	16	17	18	19	20	21	22	
																								23	
Confined to the CRU		X	X	X	X	X	X	X	X	X	X	X	X	X	X	X	X	X	X	X	X	X	X	X	
Inclusion/Exclusion Criteria	X	X																							
Informed Consent	X																								
Demographics	X																								
Medical History	X	X ^b																							
Height/Weight/BMI	X	X ^c																							
eGFR	X	X																							
Genotyping	X																								
Physical Examination ^d		X																							X
12-lead ECG ^e	X	X	X			X	X					X		X	X			X						X	
Vital Sign Measurements ^{f,g,h}	X	X	X			X	X					X		X	X			X						X	
HDYF? Inquiry ⁱ	X	X	X	X	X	X	X	X	X	X	X	X	X	X	X	X	X	X	X	X	X	X	X	X	
AEs/SAEs ^j	X	X	X	X	X	X	X	X	X	X	X	X	X	X	X	X	X	X	X	X	X	X	X	X	
Probe Drug Cocktail Dosing ^k			X															X							
LOXO-305 Dosing ^l						X	X	X	X	X	X	X	X	X	X	X	X	X	X	X	X	X	X		
CCI																									
Clinical Laboratory Evaluations ^o	X	X	X			X						X		X	X			X	X	X					
Hepatitis and HIV Screen	X																								
COVID-19 Test ^p	X	X																							
HbA1c Test	X																								
Drug Screen ^q	X	X																							
Prior and Concomitant Medications ^r	X	X	X	X	X	X	X	X	X	X	X	X	X	X	X	X	X	X	X	X	X	X	X	X	
Serum Pregnancy Test ^s	X	X																			X	X			
FSH Test ^t	X																								
TSH Test	X																								

Abbreviations: AE = adverse event; BMI = body mass index; BP = blood pressure; COVID-19 = SARS-CoV-2; CRF = Case Report Form; CRU = Clinical Research Unit; ECG = electrocardiogram; eGFR = estimated glomerular filtration rate; EOS = End of Study; EOT = End of Treatment; ET = Early Termination; FSH = follicle-stimulating hormone; HbA1c = hemoglobin A1c; HDYF? = How Do You Feel?; HIV = human immunodeficiency virus; ICF = Informed Consent Form; PK = pharmacokinetic; SAE = serious adverse event; TSH = thyroid-stimulating hormone; UA = urinalysis.

- a. For details on study procedures, see [Section 7](#).
- b. Interim medical history only.
- c. Height collected at Screening only; BMI calculated based on Screening height.
- d. A complete physical examination will be performed at Check-in (Day -1). An abbreviated physical examination will be performed at Day 23 (EOT) or at ET.
- e. 12-lead ECGs will be obtained at Screening and Check-in (Day -1), Day 1 (predose), Day 5 (96 hours postdose on Day 1), Day 6 (predose and 2 hours postdose), Day 12 (predose), Day 15 (predose and 2 hours postdose), Day 17 (predose), and Day 20 (24 hours postdose on Day 19), and Day 23 (96 hours postdose on Day 19 [EOT]) or ET. 12-lead ECGs will be collected after the subject has rested in the supine position for at least 10 minutes. When scheduled at the same time as PK blood draws, 12-lead ECGs will be obtained prior to and as close as possible to having blood drawn. The allowed sampling window for 12-lead ECGs is \pm 30 minutes from the nominal timepoint for all postdose 12-lead ECGs and no less than 10 minutes prior to dosing for predose 12-lead ECGs.
- f. Vital sign measurements (supine BP and pulse rate) will be obtained at Screening, Check-in (Day -1), Day 1 (predose), Day 5 (96 hours postdose on Day 1), Day 6 (predose and 2 hours postdose), Day 12 (predose), Day 15 (predose and 2 hours postdose), Day 17 (predose), and Day 20 (24 hours postdose on Day 19), and Day 23 (96 hours postdose on Day 19 [EOT]) or ET. Blood pressure and pulse rate will be measured using the same arm for each reading after the subject has been supine for at least 5 minutes. When scheduled at the same time as PK blood draws, vital sign measurements should be carried out prior to and as close as possible to having blood drawn. The allowed sampling window for vital sign measurements is \pm 30 minutes from the nominal timepoint for all postdose vital sign measurements and no less than 10 minutes prior to dosing for predose vital sign measurements.
- g. Respiratory rate and body temperature will be obtained at Screening, Check-in (Day -1), and Day 23 (96 hours postdose on Day 19 [EOT]) or ET.
- h. Oxygen saturation will be measured via pulse oximetry at Screening, Check-in (Day -1), predose on Day 1, and Day 23 (96 hours postdose on Day 19 [EOT]) or ET. The allowed sampling window for oxygen saturation measurements is \pm 30 minutes from the nominal timepoint for all postdose oxygen saturation measurements and no less than 10 minutes prior to dosing for predose oxygen saturation measurements.
- i. A HDYF? inquiry will be performed at Screening (after the ICF is signed), at Check-in (Day -1), at each postdose vital sign measurement, and at an appropriate time for all other days.
- j. Adverse events and SAEs will be collected beginning at informed consent. Adverse events will be recorded throughout the study (ie, from signing of the ICF until EOS, or until ET if the subject discontinues from the study and does not complete a follow-up phone call), either as subject medical history (if the event is reported as beginning prior to signing of the ICF or if the event occurs prior to study drug administration on Day 1 and is assessed as not related to study procedures by the Investigator [or designee]) or as AEs (if the event occurs after signing of the ICF but prior to study drug administration on Day 1 and is assessed by the Investigator [or designee] as related to study procedures, or if the event occurs after study drug administration on Day 1 through EOT or ET through EOS, only AEs assessed as related to study drug are to be recorded. All SAEs that develop from the time of ICF signing until EOS (or ET if the subject discontinues from the study and does not complete a follow-up phone call) are to be reported.
- k. On Day 1 and Day 15, the probe drug cocktail (200 mg caffeine [tablet], 40 mg omeprazole [capsule], and 10 mg warfarin [tablet]) and 10 mg vitamin K (tablets) will be administered orally in the morning following a fast of at least 10 hours prior to dosing and 2 hours postdose (with water restricted for 1 hour prior to and 1 hour postdose administration).
- l. On Day 6 through Day 19, oral doses of 200 mg LOXO-305 will be administered QD in the morning at the actual time of the Day 1 probe drug cocktail dosing (\pm 1 hour). On Days 7 through 11, and Days 13, 14, 16, 18, and 19, subjects will be fasted for at least 2 hours predose and 1 hour postdose. On days where clinical laboratory evaluations are performed (Day 2, Day 6, Day 12, and Day 17) subjects will be fasted for 8 hours predose and 1 hour postdose. On Day 15, 200 mg LOXO-305 will be coadministered with probe drug cocktail (200 mg caffeine [tablet], 40 mg omeprazole [capsule], and 10 mg warfarin [tablet]) and 10 mg vitamin K (tablets) in the morning at the actual time of the Day 1 probe drug cocktail dosing (\pm 1 hour), following a fast of 10 hours prior to dosing and 2 hours postdose (with water restricted for 1 hour prior to and 1 hour postdose).
- m. **CCI**

n. **CCI**

- o. Clinical chemistry panel (fasted for at least 8 hours), coagulation parameters, hematology panel, and UA will be performed at Screening, Check-in (Day -1), Day 2 (24 hours postdose on Day 1), Day 6 (predose), Day 12 (predose), Day 15 (predose), Day 17 (predose), Day 20 (24 hours postdose on Day 19), and Day 22 (72 hours postdose on Day 19, if the subject completes the study [EOT]), or on the day of ET. At ET or the day before EOT (Day 22), subjects are not required to be fasted prior to clinical laboratory evaluations.
- p. Testing for COVID-19 will be conducted at a minimum at Screening and Check-in (Day -1). Testing for COVID-19 may also be conducted periodically during the subject's CRU confinement, at the discretion of the Investigator (or designee). Tests will be performed by rapid polymerase chain reaction or equivalent.
- q. Urine drug screen for drugs of abuse (including cotinine) and alcohol screen (urine or breath).
- r. Prior and concomitant medication administration will be recorded beginning at informed consent. In addition, all Investigator-approved prescription and over-the-counter medications taken by a subject within 14 days or 5 half-lives (if known), whichever is longer, prior to Day 1 will be recorded on the subject's electronic CRF.
- s. Female subjects only. Performed at Screening, Check-in (Day -1), and Day 22 (72 hours postdose on Day 19), if the subject completes the study (EOT) or on the day of ET.
- t. Post-menopausal female subjects only.
- u. End of Treatment is defined as when the subject is released from the CRU following completion of all assessments through Day 23. Early Termination is defined as when the subject is released from the CRU if the subject terminates the study early. Vital sign measurements, ECG, and abbreviated physical examination results are to be available for review by the Investigator (or designee) prior to subject release from the CRU on Day 23 (EOT) or ET. Clinical laboratory results (for clinical chemistry, hematology, coagulation, and UA) and serum pregnancy test results (female subjects only) are to be available for review by the Investigator (or designee) prior to subject release from the CRU at the EOT visit and prior to subject release from the CRU at the ET visit if available.
- v. To be conducted 7 days (\pm 2 days) following EOT or ET. End of Study is defined as when the subject is contacted by the CRU for a follow-up phone call 7 days (\pm 2 days) after the EOT visit or ET visit to determine if any SAE or study drug-related AE has occurred since the EOT or ET visit. All subjects who received LOXO-305 or probe drug cocktail (including subjects who are terminated early) will receive a follow-up phone call.
- w. Denotes predose sample collection only.

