4.2. Check-in Procedures (Day -1)

At Check-in (Day -1), subjects will report to the CRU and the following procedures will be performed:

1. Review of inclusion/exclusion criteria
2. Interim medical history, including concomitant medication(s)

3. Weight and BMI
4. Complete physical examination ([Section 7.3.5](#))
5. 12-lead ECG measured after the subject has been resting in the supine position for at least 10 minutes ([Section 7.3.4](#))
6. Vital sign measurements (including body temperature, respiratory rate, oxygen saturation, and supine BP and pulse rate [measured after the subject has been supine for at least 5 minutes]; [Section 7.3.3](#))
7. HDYF? inquiry, AE, SAE, and concomitant medication evaluations ([Section 7.3.1](#))
8. Clinical laboratory evaluations ([Section 7.3.2](#); clinical chemistry panel [fasted at least 8 hours], coagulation parameters, hematology panel, and UA; [Appendix 2](#))
9. Screen for COVID-19 via PCR test (or equivalent; [Appendix 2](#))
10. Urine drug screen for selected drugs of abuse (including cotinine) and alcohol screen (breath or urine; [Appendix 2](#))
11. eGFR calculated using the CKD-EPI equation ([Appendix 2](#))
12. Serum pregnancy test (for female subjects only; [Appendix 2](#))
13. Compliance with concomitant medications and exclusionary restrictions ([Section 6](#))

For subjects to continue their participation in the study, the inclusion/exclusion criteria must continue to be met at Check-in (Day -1 [as appropriate; #1, [Section 4.2](#)]). In addition, continued compliance with concomitant medication and other restrictions will be verified.

The Sponsor will review medical history and all screening evaluations for potential subjects prior to Check-in (Day -1). Prior to dosing, the Sponsor will provide approval of subjects selected for enrollment by the Investigator (or designee).

Subjects who meet all the inclusion criteria and for whom none of the exclusion criteria apply will be eligible to be enrolled into the study. Safety evaluations may be repeated at the discretion of the Investigator (or designee) or Sponsor.

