7.3.2. Clinical Laboratory Evaluations

Clinical laboratory evaluations (clinical chemistry panel [fasted at least 8 hours; at ET or the day before EOT, subjects are not required to be fasted prior to clinical laboratory evaluations], coagulation parameters, hematology panel, TSH [Screening only], HbA1c [Screening only], eGFR [Screening and Check-in (Day -1)], and UA) will be collected at the timepoints specified in [Appendix 4](#).

Screens for HCV antibody, HBsAg, HBV IgM core antibody, and HIV antibody will be performed at Screening.

Testing for COVID-19 via PCR (or equivalent) will be performed at the timepoints specified in [Appendix 4](#). Testing for COVID-19 may also be conducted periodically during the subject's CRU confinement, at the discretion of the Investigator (or designee). Further details regarding COVID-19 testing (including procedures for subjects who test positive at any time throughout CRU confinement) are specified in a separate document.

A urine drug screen for selected drugs of abuse (including cotinine) and an alcohol screen (urine or breath) will be performed at Screening and repeated at Check-in (Day -1) for all subjects. A serum qualitative pregnancy test (female subjects only [serum quantitative may be used for confirmation, if needed]) and an FSH test (post-menopausal female subjects only) will be performed at the timepoints specified in [Appendix 4](#).

The number of blood samples and total blood volume required for clinical laboratory evaluations are presented in [Appendix 3](#). A list of the specific evaluations is in [Appendix 2](#).

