8.6.2. Clinical Laboratory Parameters

All clinical laboratory parameters, with changes from baseline, will be listed; any value outside the clinical reference range will be flagged, and whether the out of range value was deemed clinically significant or not clinically significant will be indicated.

The observed results and change from baseline for clinical chemistry, hematology, and coagulation parameters will be summarized descriptively by timepoint. Values recorded as $\text{<}x$, $\leq x$, $\geq x$, or $\text{>}x$ will be displayed in the listings as recorded. For the derivation of listing flags, calculation of summary statistics, $\text{<}x$ and $\leq x$ values will be set to 0, whereas $\geq x$ and $\text{>}x$ values will be set to x.

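### The scheduled Day 22 chemistry sample may be taken unfasted, yet its change from a fasted baseline is summarised with no marker of fasting status

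*Protocol*

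**What the plan says.** Protocol Appendix 4, footnote o, sets the general rule: "Clinical chemistry panel (fasted for at least 8 hours), coagulation parameters, hematology panel, and UA will be performed at Screening, Check-in (Day -1") and at the later laboratory days. The list ends with "Day 20 (24 hours postdose on Day 19), and Day 22 (72 hours postdose on Day 19, if the subject completes the study [EOT"]). The same footnote then makes the exception: "At ET or the day before EOT (Day 22), subjects are not required to be fasted prior to clinical laboratory evaluations". Protocol 7.3.2 repeats it: "at ET or the day before EOT, subjects are not required to be fasted prior to clinical laboratory evaluations". With two matching statements, the waiver is intended and is not a slip.

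Appendix 2 heads the chemistry panel as fasted and includes glucose and triglycerides.

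On the analysis side, SAP 8.6.2 states: "The observed results and change from baseline for clinical chemistry, hematology, and coagulation parameters will be summarized descriptively by timepoint". SAP 8.1.3 takes baseline as the last non-missing value before Day 1 dosing. SAP 8.1.1 leaves early-termination (ET) data out of summary statistics because they belong to no scheduled timepoint. Day 22 is a scheduled timepoint for completers, so it stays in. Nothing in the SAP text records, flags or separates samples by fasting status.

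**The concern.** A change from baseline reads cleanly only if both samples were taken under the same conditions. At Day 22 the plan allows a fed value to be compared with a fasted baseline, and the planned table would not show that this had happened.

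Day 22 is 72 hours after the last LOXO-305 dose and is the last scheduled laboratory sample; the later follow-up is a phone call. It is therefore the natural place to look for recovery or a late change. In food-sensitive analytes, a rise there could come from a meal, and a fall back towards baseline could be masked by one. Subjects eat a standard diet at scheduled times (Protocol 6.2). If the draw follows a meal, the shift is likely to be shared across subjects, so it would appear as bias and not only as noise.

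Out-of-range flags and the clinical-significance classification in SAP 8.6.2 would be applied to the same values.

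**Working it through.** There is no stated figure to reproduce: the sample size was chosen without statistical considerations and no safety inference is planned. The check is a side-by-side reading, followed by an illustration of size.

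**1. Fasting state by scheduled timepoint**

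| Timepoint | Fasting rule | Source (Protocol) |
|---|---|---|
| Screening | at least 8 h | 4.1; footnote o |
| Check-in (Day -1) | "clinical chemistry panel [fasted at least 8 hours], coagulation parameters, hematology panel, and UA" | 4.2 |
| Days 2, 6, 12, 17 | "Day 2, Day 6, Day 12, and Day 17) subjects will be fasted for 8 hours predose and 1 hour postdose" | footnote l |
| Day 15 | "following a fast of 10 hours prior to dosing and 2 hours postdose" | footnote l |
| Day 20 | at least 8 h (general rule) | footnote o |
| Day 22 | waived | footnote o; 7.3.2 |

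That makes 2 + 4 + 1 + 1 + 1 = 9 timepoints, which agrees with the 9 chemistry samples in Appendix 3. Seven are post-baseline; six of these are fasted and one (Day 22) need not be. Footnote o lists no Day 1 predose panel, so baseline is normally the fasted Check-in sample.

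**2. What Day 22 measures**

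Table 1 of the protocol gives a half-life of 19.9 h at 200 mg QD in patients, and 17.4 to 30.1 h across dose levels. The fraction remaining after time t is 2^(-t/half-life).

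- At 72 h (Day 22): 2^(-72/19.9) = 8.1% (range 5.7% to 19.1%).
- At 24 h (Day 20): 2^(-24/19.9) = 43.3% (range 38.4% to 57.5%).

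Day 22 is thus mostly a recovery reading. Day 20 is fasted but taken with much more drug present.

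**3. Size of a possible artefact**

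Let f be the share of subjects sampled unfasted and m the mean meal shift. The bias in the mean change is f × m. The documents give neither quantity, nor an SD.

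Assumptions for glucose: m = 10 to 30 mg/dL, the same in every fed subject; SD of change = 10 mg/dL; n = 16 (the maximum in Protocol 8.1).

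- All fed (f = 1): SE = 10/√16 = 2.5 mg/dL. The bias is 10/2.5 = 4 SE to 30/2.5 = 12 SE.
- Half fed (f = 0.5): mixing fed and fasted subjects adds variance f(1 − f)m² = 0.25m².
  - m = 10: SD = √(100 + 25) = 11.2, SE = 2.8, bias = 5, giving 1.8 SE.
  - m = 30: SD = √(100 + 225) = 18.0, SE = 4.5, bias = 15, giving 3.3 SE.
- All fasted (f = 0): bias = 0.

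Milder assumptions give less. With m between 0.25 and 1 SD of the change score, the bias runs from 0.25 × 0.25 = 0.06 SD (0.25 SE) when a quarter are fed to 1 SD (4 SE) when all are fed. At the lower end the added spread is negligible: √(1 + 0.1875 × 0.0625) = 1.006.

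**The case against.** The strongest reply is that the waiver is deliberate, consistent and harmless in practice. No document says that subjects eat before the Day 22 draw. Subjects stay in the unit until Day 23, safety evaluations may be repeated at the discretion of the investigator or sponsor (Protocol 7.3), and a subject may be kept longer (7.3.1). An odd value can therefore be checked fasted before release. The discharge concern in Protocol 1.6 is a fall in white cells, which is read from the hematology panel, where no fast is specified. Only a few chemistry analytes are food-sensitive, and no test or decision rule rests on them, so standard errors are only a rough yardstick.

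Most of this stands, and it limits the point to a minor one. It does not remove it. A fasted repeat helps the individual review, but SAP 8.1.2 treats any extra laboratory value as unscheduled and excludes post-dose unscheduled values from calculations. The Day 22 summary would still carry the original value.

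Three stronger readings are tempting, and the documents do not support them:

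- A reader might infer that Day 22 is the only laboratory value after treatment ends. Day 20 is also after the last dose on Day 19, and it is fasted.
- A reader might infer that the Day 22 change is certainly confounded. The waiver permits an unfasted sample but does not require one.
- A reader might halve the all-fed figures and quote 2 to 6 SE when half are fed. That leaves out the extra spread from mixing fed and fasted subjects; on the same assumptions the range is about 1.8 to 3.3 SE.

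**Conclusion.** The point holds as a minor, avoidable comparability problem in a planned safety table. Day 22 is the one summarised chemistry timepoint that may set an unfasted value against a fasted baseline, and the SAP gives the reader no means of seeing it. ET samples share the waiver but are not summarised, so they do not add to the problem.

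The size cannot be derived from the documents. The figures above depend wholly on the assumed meal shift, SD and share fed, and they fall to zero if everyone happens to be fasted. The consequence is confined to descriptive summaries and flags for food-sensitive analytes; the primary PK analysis is unaffected. Day 20 offers a partial fasted cross-check, but at 24 hours it cannot stand in for the 72-hour recovery reading.

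**What to change.** In Protocol 7.3.2 and Appendix 4, footnote o, restrict the fasting waiver to ET samples, so that the scheduled Day 22 chemistry sample follows the same fast of at least 8 hours as Day 20. Keeping the waiver for unplanned ET samples is reasonable, since their timing cannot be arranged in advance and SAP 8.1.1 does not summarise them.

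The cost is one more overnight fast for subjects already confined to the unit, and two edited sentences.

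If the waiver is kept, record fasting status at Day 22. In the listings and the SAP 8.6.2 summary table, mark the food-sensitive Day 22 analytes as not like-for-like with the fasted baseline. This leaves conduct almost unchanged and makes the limitation visible, but it does not remove the bias. The table shells are not part of the public documents, so whether such a footnote already exists cannot be checked.

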12. APPENDICES	21

LIST OF ABBREVIATIONS

Abbreviations pertain to the statistical analysis plan (SAP) only (not the tables, figures, and listings [TFLs]).

%AUC _{extrap}	percentage extrapolation for AUC _{0-inf}
AUC ₀₋₂₄	area under the concentration-time curve from hour 0 to 24 hours postdose
AUC _{0-t}	area under the concentration-time curve from hour 0 to the last measurable concentration
AUC _{0-inf}	area under the concentration-time curve from hour 0 extrapolated to infinity
ADaM	analysis data model
AE	adverse event
BLQ	below the limit of quantification
CDISC	Clinical Data Interchange Standards Consortium
CI	confidence interval
CL/F	apparent systemic clearance
C _{max}	maximum observed plasma concentration
CRU	Clinical Research Unit
CSR	clinical study report
CTCAE	Common Terminology Criteria for Adverse Events
CV	coefficient of variation
CYP	cytochrome P450
ECG	electrocardiogram
EOS	End of Study
EOT	End of Treatment
ET	Early Termination
Geom CV	geometric CV
Geom Mean	geometric mean
ICF	Informed Consent Form
ICH	International Council for/Conference on Harmonisation of Technical Requirements for Registration of Pharmaceuticals for Human Use
λ_z	apparent terminal elimination rate constant
λ_z Lower	start of exponential fit
λ_z N	number of data points included in the log-linear regression
λ_z Span Ratio	time period over which λ_z was determined as a ratio of $t_{1/2}$
λ_z Upper	end of exponential fit
LSM	least squares mean
λ_z	apparent terminal elimination rate constant

MedDRA	Medical Dictionary for Regulatory Activities
MRAUC ₀₋₂₄	ratio of paraxanthine AUC ₀₋₂₄ to caffeine AUC ₀₋₂₄
MRT _{inf}	mean residence time extrapolated to infinity
NC	not calculated
NR	not reported
PK	pharmacokinetic(s)
QD	once daily
QTcF	QT interval corrected for heart rate using Fridericia's formula
R ² -adj	adjusted coefficient for determination of exponential fit
SAE	serious adverse event
SAP	statistical analysis plan
SD	standard deviation
t _{1/2}	apparent plasma terminal elimination half-life
TEAE	treatment-emergent adverse event
TFL	table, figure, and listing
t _{max}	time to maximum observed plasma concentration
V _z /F	apparent volume of distribution at the terminal phase
WHODrug	World Health Organization Drug Dictionary

